8.2.1.2. Safety Analysis Set

The primary analysis set for safety analyses is defined as all subjects that received at least one dose of study drug.

There will be 2 safety analysis sets: the E/C/F/TAF safety analysis set which includes subjects who received at least one dose of E/C/F/TAF study drug, and the B/F/TAF safety analysis set which includes subjects who received at least one dose of B/F/TAF study drug.

All data collected during treatment will be included in the safety summaries.

8.2.1.3. Pharmacokinetics

The Pharmacokinetic (PK) analysis set will include all subjects for whom concentration data of any one analyte (e.g., BIC, TAF, EVG, COBI, TFV and/or FTC) of interest are available.

There may be 2 PK analysis sets: the E/C/F/TAF PK analysis set which includes subjects who received at least one dose of E/C/F/TAF study drug, and the B/F/TAF PK analysis set which includes subjects who received at least one dose of B/F/TAF study drug.

CCI

8.3. Demographic Data and Baseline Characteristics

Demographic and baseline measurements will be summarized using standard descriptive methods.

Demographic summaries will include sex, race/ethnicity and age.

Baseline data will include a summary of body weight, height, body mass index and HIV-1 infection.

8.4. Primary and Secondary Analysis

8.4.1. Primary Analysis

The primary endpoint is the incidence of treatment-emergent grade 3 or higher adverse events up to Week 48 in subjects receiving E/C/F/TAF. Treatment-emergent adverse events are defined in Section 8.5.2.

8.4.2. Secondary Analyses

The proportion of subjects receiving E/C/F/TAF who achieve HIV-1 RNA < 50 copies/mL at Weeks 24, 48, and 96 will be computed using the FDA snapshot algorithm. CCI [REDACTED]

8.5. Safety Analysis

All safety analyses will be performed using the safety analysis sets.

All safety data collected on or after the date that study drug was first administered up to the date of last dose of study drug plus 30 days will be summarized. Data for pre-treatment period and the period post the date of last dose plus 30 days will be included in data listings.

8.5.1. Extent of Exposure

A subject's extent of exposure to study drug will be generated from the study drug administration data. Exposure data will be summarized.

Duration of exposure to study drug will be expressed as the number of weeks between the first and last dose of each study drug, inclusive, regardless of temporary interruptions in study drug administration, and summarized. Dosing information for individual subjects will be listed.

8.5.2. Adverse Events

Clinical and laboratory adverse events will be coded using the Medical Dictionary for Regulatory Activities (MedDRA). System Organ Class (SOC), High-Level Group Term (HLGT), High-Level Term (HLT), Preferred Term (PT), and Lower-Level Term (LLT) will be attached to the clinical database.

Treatment-emergent adverse events are adverse events that meet one of the following criteria:

- Adverse events with onset dates on or after the first dose date of study drug, and no later than 30 days after permanent discontinuation of study drug, or
- Adverse events that result in permanent study drug discontinuation

Summaries (number and percentage of subjects) of treatment-emergent adverse events (by SOC, HLT [if applicable], and PT) will be provided. Additional summaries will include summaries for adverse events by grade, Investigator's assessment of relationship to study drug, and effect on study drug dosing.

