6.5.3. Criteria for Discontinuation of Study Treatment

Study drug may be discontinued in the following instances:

- Intercurrent illness that would, in the judgment of the investigator, affect assessments of clinical status to a significant degree. Following resolution of intercurrent illness, the subject may resume study dosing at the discretion of the investigator.
- Unacceptable toxicity, or toxicity that, in the judgment of the investigator, compromises the ability to continue study-specific procedures or is considered to not be in the subject's best interest
- Lack of efficacy
- Subject request to discontinue for any reason
- Subject noncompliance
- Pregnancy during the study; refer to [Appendix 7](#)
- Discontinuation of the study at the request of Gilead, a regulatory agency or an institutional review board or independent ethics committee (IRB/IEC)

[figure not shown]

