7.1.2. Serious Adverse Events

A **serious adverse event** (SAE) is defined as an event that, at any dose, results in the following:

- Death
- Life-threatening (Note: The term “life-threatening” in the definition of “serious” refers to an event in which the subject was at risk of death at the time of the event; it does not refer to an event that hypothetically might have caused death if it were more severe.)
- In-patient hospitalization or prolongation of existing hospitalization
- Persistent or significant disability/incapacity

- A congenital anomaly/birth defect
- A medically important event or reaction: such events may not be immediately life-threatening or result in death or hospitalization but may jeopardize the subject or may require intervention to prevent one of the other outcomes constituting SAEs. Medical and scientific judgment must be exercised to determine whether such an event is a reportable under expedited reporting rules. Examples of medically important events include intensive treatment in an emergency room or at home for allergic bronchospasm; blood dyscrasias or convulsions that do not result in hospitalization; and development of drug dependency or drug abuse. For the avoidance of doubt, infections resulting from contaminated medicinal product will be considered a medically important event and subject to expedited reporting requirements.

7.1.3. Clinical Laboratory Abnormalities and Other Abnormal Assessments as Adverse Events or Serious Adverse Events

Laboratory abnormalities without clinical significance are not recorded as AEs or SAEs. However, laboratory abnormalities (e.g., clinical chemistry, hematology, and urinalysis) that require medical or surgical intervention or lead to study drug interruption, modification, or discontinuation must be recorded as an AE, as well as an SAE, if applicable. In addition, laboratory or other abnormal assessments (e.g., electrocardiogram, x-rays, vital signs) that are associated with signs and/or symptoms must be recorded as an AE or SAE if they meet the definition of an AE or SAE as described in Sections 7.1.1 and 7.1.2. If the laboratory abnormality is part of a syndrome, record the syndrome or diagnosis (e.g., anemia), not the laboratory result (i.e., decreased hemoglobin).

For specific information on handling of clinical laboratory abnormalities in this study, please refer to Section 7.6.

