7.6. Toxicity Management

All clinical and clinically significant laboratory toxicities will be managed according to uniform guidelines detailed in [Appendix 5](#) as outlined below.

- All clinically significant Grades 3 and 4 laboratory abnormalities should be repeated within 3 calendar days to confirm toxicity grade. Confirmation of toxicity grade is required prior to the next dose of study drug for any Grade 3 and 4 laboratory abnormality that in the opinion of the Investigator is clinically significant and may pose a risk to the subject’s safety.
- Clinical events and clinically significant laboratory abnormalities will be graded according to the GSI Grading Scale for Severity of Adverse Events and Laboratory Abnormalities (refer to [Appendix 6](#)).
- Any questions regarding toxicity management should be directed to the Medical Monitor.

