7.6.2. Grade 3 Laboratory Abnormality or Clinical Event

- For Grade 3 clinically significant laboratory abnormality or clinical event, study drug may be continued if the event is considered to be unrelated to study drug.
- For a Grade 3 clinical event, or clinically significant laboratory abnormality confirmed by repeat testing, that is considered to be related to study drug, study drug should be withheld until the toxicity returns to \leq Grade 2.
- If a laboratory abnormality recurs to \geq Grade 3 following re-challenge with study drug and is considered related to study drug, then study drug should be permanently discontinued and the subject managed according to local practice. Recurrence of laboratory abnormalities considered unrelated to study drug may not require permanent discontinuation.

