4.2.3. Adherence with Study Drug

Study drug adherence will be computed based on pill counts. The numbers of pills of study drug dispensed and returned are captured on the Study Drug Accountability eCRF.

Adherence (%) to E/C/F/TAF study drug will be calculated as follows:

$$\text{Adherence (\%)} = 100 \times \frac{\text{Total No. of pills taken}}{\text{Total No. of pills prescribed}}$$
$$100 \times \frac{\sum \text{No. of pills taken at each dispensing period}^{[1]}}{\sum \text{No. of pills prescribed at each dispensing period}^{[2]}}$$

- [1] Number of pills taken at a distinct dispensing period for a study drug is calculated as the minimum of (a) the daily number of pills prescribed for the study drug multiplied by the duration of treatment at the dispensing period, and (b) the number of pills taken for the study drug (number of pills dispensed minus the number of pills returned). Total number of pills taken is determined by summing the number of pills taken from all evaluable dispensing periods.
- [2] Number of pills prescribed at a distinct dispensing period for a study drug is calculated as the daily number of pills prescribed for the study drug multiplied by the duration of treatment at the dispensing period. Total number of pills prescribed is determined by summing the number of pills prescribed from all evaluable dispensing periods.

The duration of treatment at each dispensing period is calculated as the minimum of (a) the last returned date of study drug at a dispensing period, (b) date of premature discontinuation of the study drug, and (c) next pill dispensing date of the study drug, minus dispensing date of the study drug.

The next pill dispensing date is the following dispensing date of the study drug regardless of the bottle return date.

For a record where the number of pills returned was missing (with “Yes” answered for “Was Bottle returned?” question), it is assumed the number of pills returned was zero. If the number of pills dispensed was missing or any study drug bottle was not returned, or the bottle return status was unknown, then all records in that dispensing period will be excluded from both denominator and numerator calculation.

Adherence will be calculated using all data from the entire dosing period up to the date of permanent discontinuation of the E/C/F/TAF study drug for subjects who prematurely discontinued study drug or completed E/C/F/TAF study drug.

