8.3.6. Summaries of Adverse Events and Deaths

The number and percentage of subjects who experienced at least 1 TEAE will be provided and summarized by SOC, HLT, and PT separately for the E/C/F/TAF Safety Analysis Set and B/F/TAF Safety Analysis Set. For other AEs described below, summaries will be provided by SOC and PT separately for the E/C/F/TAF Safety Analysis Set and B/F/TAF Safety Analysis Set:

- Any Grade 2, 3, or 4 treatment-emergent AE
- Any Grade 3 or 4 treatment-emergent AE
- All treatment-emergent study-drug-related AEs
- Any Grade 2, 3, or 4 treatment-emergent study-drug-related AE
- Any Grade 3 or 4 treatment-emergent study-drug-related AE
- All treatment-emergent SAEs
- All treatment-emergent study-drug-related SAEs
- All treatment-emergent AEs that caused premature discontinuation from study drug

A brief, high-level summary of AEs described above will be provided by the number and percentage of subjects who experienced the above AEs. Treatment-emergent deaths observed in the study will also be included in this summary.

For the E/C/F/TAF Safety Analysis Set summary, treatment-emergent death refers to a death that occurred between the first E/C/F/TAF dose date and the last E/C/F/TAF dose date plus 30 days (inclusive) for subjects who do not participate in the B/F/TAF OL extension phase or the day prior to the date of the first B/F/TAF study drug dose for subjects who participate in the B/F/TAF OL extension phase.

For the B/F/TAF Safety Analysis Set summary, treatment-emergent death refers to a death that occurred between the first B/F/TAF dose date and the last B/F/TAF dose date plus 30 days (inclusive).

Multiple events will be counted only once per subject in each summary. Adverse events will be summarized and listed first in alphabetical order of SOC and HLT within each SOC (if applicable), and then by PT in descending order of total frequency within each SOC. For summaries by severity grade, the most severe grade will be used for those AEs that occurred more than once in an individual subject during the study.

In addition to the above summary tables, all treatment-emergent AEs will be summarized by PT only, in descending order of total frequency.

In addition, data listings will be provided for the following:

- All AEs (with a variable indicating whether the event is treatment-emergent)
- Grade 3 and 4 AEs
- Study-drug-related AEs
- SAEs
- Study-drug-related SAEs
- Deaths reported

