8.10. Changes From Protocol-Specified Safety Analyses

No change from protocol-specified safety analyses is planned.

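### No planned summary identifies adverse events that led to temporary interruption of study drug, and the adherence formula counts held days as missed pills when the subject keeps the bottle

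*Protocol*

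**What the plan says.** **Where dosing can pause.** For a related Grade 3 event, or a related and confirmed Grade 3 laboratory abnormality, protocol 7.6.2 says "study drug should be withheld until the toxicity returns to" Grade 2 or lower. Protocol 6.5.3 covers stopping for another illness: "Following resolution of intercurrent illness, the subject may resume study dosing at the discretion of the investigator". Protocol 7.6 adds a possible short gap: "Confirmation of toxicity grade is required prior to the next dose of study drug for any Grade 3 and 4 laboratory abnormality" that the investigator judges clinically significant and a possible risk to the subject.

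**How pauses are recorded and summarised.** Protocol 7.1.3 says that laboratory abnormalities that "lead to study drug interruption, modification, or discontinuation must be recorded as an AE". It therefore names interruption and discontinuation as separate outcomes. Protocol 8.5.2 adds to the main tables summaries by grade and by the investigator's "assessment of relationship to study drug, and effect on study drug dosing".

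**What the SAP plans.** The one dosing-related item among the SAP 8.3.6 tables is "All treatment-emergent AEs that caused premature discontinuation from study drug". The matching listing has the same scope. SAP 8.10 states: "No change from protocol-specified safety analyses is planned".

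**Adherence.** In SAP 4.2.3 the number of pills prescribed in a dispensing period is "calculated as the daily number of pills prescribed for the study drug multiplied by the duration of treatment at the dispensing period". Pills taken are those dispensed minus those returned, capped at the number prescribed. A dispensing period ends at the earliest of drug return, premature discontinuation and the next dispensing.

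**The concern.** Safety and tolerability is the primary objective for E/C/F/TAF and a secondary objective for B/F/TAF. Whether an adverse event made the investigator pause the drug is direct evidence on tolerability, and the protocol said it would be summarised. The final tables will show which events ended treatment but not which ones paused it. A reader of SAP 8.10 would not know that anything had been left out.

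The adherence formula raises a related but smaller issue. A subject who follows an instruction to stop and later resumes may be scored as having missed those doses. The adherence table then mixes instructed holds with patient lapses, and nothing else in the SAP's tables separates them.

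**Working it through.** The plan states no figure on this point, so there is none to reproduce. The check compares the texts and then applies the SAP formula.

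**Step 1: is interruption covered elsewhere?**
- SAP 8.3.6: discontinuation only, in tables and in the dosing-specific listing. The listing of all events is not said to show the action taken with study drug.
- SAP 4.2.1 and 4.2.2: exposure runs from first to last dose without deducting breaks. The Kaplan-Meier analysis in 4.2.1 concerns premature discontinuation.
- Protocol 8.5.1: promises a listing of individual dosing, which is not a summary of events by dosing effect.

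The discontinuation table meets part of the promise in protocol 8.5.2. The interruption part has no counterpart in the SAP.

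**Step 2: how a hold enters adherence.** Take one tablet a day, D days of treatment and h held days. Assume the bottle is kept during the hold and every other dose is taken.
- Pills prescribed = D. Pills taken = min(D, D − h) = D − h.
- SAP adherence = 100 × (D − h)/D.
- With held days removed from both the cap and the denominator: 100 × (D − h)/(D − h) = 100%.

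D comes from the design: 96 × 7 = 672 days of E/C/F/TAF and 48 × 7 = 336 days of B/F/TAF. The values of h are assumptions.

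| Held days | D = 672 | D = 336 |
|---|---|---|
| 3 | 669/672 = 99.6% | 333/336 = 99.1% |
| 7 | 665/672 = 99.0% | 329/336 = 97.9% |
| 14 | 658/672 = 97.9% | 322/336 = 95.8% |
| 28 | 644/672 = 95.8% | 308/336 = 91.7% |

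**Step 3: leaving the top category of SAP 4.2.3 (95% or more).** This needs h greater than 0.05 × D.
- D = 672: 0.05 × 672 = 33.6, so 34 days (638/672 = 94.9%).
- D = 336: 0.05 × 336 = 16.8, so 17 days (319/336 = 94.9%).

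**Step 4: sensitivity to perfect pill-taking.** Suppose the subject takes 97% of doses on days not held and has a 14-day hold.
- D = 336: 0.97 × 322/336 = 93.0%, against 97.0% with held days removed.
- D = 672: 0.97 × 658/672 = 94.98%, against 97.0%.

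The 34- and 17-day thresholds therefore hold only for subjects who miss nothing else. Others leave the top category after a shorter hold.

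**The case against.** The strongest reply is that little is lost. The hold in protocol 7.6.2 applies to related Grade 3 events, and SAP 8.3.6 has a table of related Grade 3 or 4 treatment-emergent events for both Safety Analysis Sets. Other events that led to a hold appear in the all-event, grade, relatedness and serious-event tables as they qualify. Laboratory abnormalities that interrupt dosing must be recorded as adverse events, so they enter those tables too. This stands: only the link to interruption is missing. A reader might infer that tolerability problems are hidden, but the documents do not support that.

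Protocol 8.5.2 does not itself use the word interruption, so the discontinuation table could be said to satisfy it. That is only partly persuasive, since protocol 7.1.3 lists interruption separately.

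The exposure definition is not a deviation, because protocol 8.5.1 specifies it in the same way.

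On adherence, three limits stand. Drug returned at the start of a hold ends the dispensing period, so that gap is not counted. Periods with an unreturned bottle are dropped altogether. Adherence is pooled over the whole dosing period, so the 70/84 = 83.3% that a 14-day hold would give within a single 84-day period is not a planned output.

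A reader might also set the interim figures in protocol 1.2.5 against each other: 29 of 55 subjects with serious events and 20 of 55 with Grade 3 or 4 events, but 3 of 55 with events leading to discontinuation. These are not counts of holds. Only 6 of 55 had any related event and no serious event was related, so holds ordered for related toxicity may have been few. Holds permitted for another illness cannot be counted from the documents.

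**Conclusion.** The point holds in a limited form. The SAP leaves out the interruption part of a summary that the protocol promised and does not declare the omission. Its adherence formula has no rule for holds, so held days count as missed when the bottle stays with the subject.

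The direction of the adherence effect follows from the formula. Its size is modest: about 1 to 4 percentage points for a hold of one to four weeks over 672 days, and about 2 to 8 points over 336 days. This assumes that the bottle is kept and all other doses are taken. The hold lengths are assumed, and the number of holds is unknown.

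It would go too far to conclude that tolerability will look materially better, or patients materially less adherent, than they were. Adherence is descriptive and not an endpoint. The primary endpoint was analysed for the Week 48 report and is not repeated under this SAP (SAP 6.1). Earlier analysis plans are not among the documents, so an interruption summary may have been produced at an interim stage. This SAP nevertheless governs the final tables for both phases.

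**What to change.** 1. **SAP 8.3.6.** Add treatment-emergent adverse events leading to temporary interruption of study drug, by system organ class and preferred term and in the high-level summary, for the E/C/F/TAF and B/F/TAF Safety Analysis Sets. At minimum, declare the omission in SAP 8.10.
2. **SAP 4.2.3.** Keep the current adherence figure. Add a supplementary line that removes recorded interruption days from both the numerator cap and the denominator, using the start and end dates on the Study Drug Administration eCRF. Limit it to investigator-directed holds if the eCRF records the reason.

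The adherence change should be a supplement and not a replacement. SAP 3.8.1 shows start dates, end dates and a box for permanent withdrawal, but no field that separates an instructed hold from a patient's own lapse.

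The cost is one extra table per phase and one extra derivation. Interruptions recorded without dates would still count as missed pills.

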8.5.3. Laboratory Evaluations

Selected laboratory data will be summarized using only observed data. Absolute values and changes from baseline at all scheduled time points will be summarized.

Graded laboratory abnormalities will be defined using the GSI Grading Scale for severity of Adverse Events and Laboratory Abnormalities ([Appendix 6](#)).

Incidence of treatment-emergent laboratory abnormalities, defined as values that increase at least one toxicity grade from baseline at any time post baseline up to the date of last dose of study drug plus 30 days, will be summarized. If baseline data are missing, then any graded abnormality (i.e., at least a Grade 1) will be considered treatment-emergent. The maximum toxicity grade will be summarized by laboratory parameter.

Laboratory abnormalities that occur before the first dose of study drug or after the subject has been discontinued from treatment plus 30 days will be included in a data listing.

8.5.4. Other Safety Evaluations

[figure not shown]
Weight will be summarized by visit.

Safety ECGs will be listed and summarized for subjects in the safety analysis sets. The number and percent of subjects with abnormal safety ECG will be summarized by visit.

8.6. Pharmacokinetic Analysis

The concentration data of any analyte (e.g., BIC, TAF, EVG, COBI, TFV and/or FTC) of interest, as applicable, will be listed.

CCI

8.7. Sample Size

A sample size of approximately 50 subjects is based on practical considerations and is considered to be sufficient to evaluate the primary objective of this study. The Grade 3 or higher AE rate in Study GS-US-292-0112 in subjects that had mild to moderate renal impairment was 8.8% at Week 48 analysis for the E/C/F/TAF arm. Therefore, with 50 subjects, and an assumed rate of Grade 3 or higher AEs being 10%, this study would provide 95% confidence for the primary endpoint to be (1.7%, 18.3%) assuming normal approximation to binomial proportions.

CCI

